4. STATISTICAL ANALYSES

4.1. General Considerations

Participant-level data will be available interactively via Reporting and Analysis Plan Improving Design and Delivery of Output Data Viewer (RAPIDO DV) at Study Analysis Complete (SAC). Only selected listings specified in the Output Programming Specification (OPS) will be created in a static fashion.

The term “Analysis Set” in the SAP will be referred to as “Population” in displays. The term “Participant” in the SAP will be referred to as “Subject” and/or “Patient” in the displays of the OPS document.

The term “Study intervention” and “Study Treatment” are used interchangeably unless specified.

A list of all planned displays will be provided in the OPS document.

Adverse event analysis will be based on GSK Core Data Standards. All AE and SAE summaries will be by SOC and PT only unless otherwise specified.

If there are more than CCI who choose to take part in the optional Bepirovirsen extension arm, then summary tables will be produced. If less than CCI choose to participate, then only listings will be produced.

4.1.1. General Methodology

Summary tables unless otherwise specified will include the following descriptive statistics at a minimum -

- For continuous data (untransformed): n, mean, standard deviation (SD), 95% CI, median, minimum, and maximum.
- For continuous data (log transformed): n, Geometric Mean (GM), 95% CI, between subject coefficient of variation (%CV_b)
- For categorical data: number and percentage of participants in each category

Where appropriate, statistical modelling will be performed, and point estimates with 95% Confidence Interval (CIs).

HBV DNA, HBsAg, and anti-HBs levels that are below the Lower Limit of Quantification (LLOQ) or target not detected (TND) will be imputed for summaries of actual values and change from baseline.

Table 1 Imputation details for LLOQ values of Biomarker

Biomarker	LLOQ	Imputing Value
HBV DNA	10 IU/mL	9.9 IU/mL
HBV DNA	20 IU/mL	19.9 IU/mL
HBsAg	0.05 IU/mL	0.04 IU/mL
anti-HBs	4 IU/mL	3.99 IU/mL

Table 2 Imputation details for TND values of Biomarker

Biomarker	Limit of Detection	Imputing Value
HBV DNA	2.4 IU/mL	2.3 IU/mL
HBcrAg	2.0 log ₁₀ U/mL	1.99 log ₁₀ U/mL
HBV RNA	309 copies/mL (Assay LOD)	308 copies/mL
anti-HBs	2.0 IU/mL	1.99 IU/mL

For all other laboratory values, if a laboratory value which is expected to have a numeric value for summary purposes, has a non-detectable level reported in the database, where the numeric value is missing, but typically a character value starting with '<x' or '>x' (or indicated as less than x or greater than x in the comment field) is present, the number of decimal places in the observed values will be used to determine how much to add or subtract in order to impute the corresponding numeric value. Similarly, if a character value starting with '<=x' or '>=x' is present, x will be used as the corresponding numeric value.

- Example 1: 2 Decimal places: = '< x' becomes $x - 0.01$
- Example 2: 1 Decimal places: = '> x' becomes $x + 0.1$
- Example 3: 0 Decimal places: = '< x' becomes $x - 1$
- Example 4: 2 Decimal places: = '<= x' becomes x
- Example 5: 1 Decimal places: = '<= x' becomes x
- Example 6: 0 Decimal places: = '<= x' becomes x

Derivation of log₁₀ Change from Baseline for HBsAg and Maximum reduction of log₁₀ HBsAg:

- Compute log₁₀ HBsAg at baseline by converting the baseline HBsAg value to its logarithm base 10 form
- For all post-baseline visits, compute corresponding log₁₀ HBsAg by converting the actual HBsAg values to their logarithm base 10 form

- Compute the change in log10 HBsAg values from baseline for each post-baseline visit as: Log10 HBsAg at post baseline - Log10 HBsAg at baseline
- Maximum reduction in log10 HBsAg value is the minimum value of the calculated change from baseline at any post-baseline visit within the specified timeframe (CCI)

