1.1.1. Primary Estimand

The primary clinical question of interest is: What is the difference in maximum reduction of HBsAg from baseline CCI in GSK3965193 vs. placebo in participants living with chronic hepatitis B infection, prior to prohibited medication use or temporary/permanent discontinuation of treatment?

Attributes of Estimand:

Variable/Endpoint	Treatment	Population	Population Summary
Maximum reduction of serum HBsAg levels from baseline CCI CCI CCI CCI	GSK3965193 and Placebo	PLWCHB treated on stable nucleos(t)ide analog (NA) therapy	Mean of maximum reduction in change from baseline over all patients in GSK3965193 and Placebo. Treatment difference (GSK3965193 – Placebo).

Intercurrent Event			Strategy	
Intercurrent Event	Details on the Intercurrent Event	Decision on the usage of data	Strategy	Rationale
Temporary or permanent discontinuation of dosing	Temporary or permanent discontinuation of IP dose include any of the following occurrences: 
 Missing 2 or more consecutive doses Permanent discontinuation from treatment Permanent discontinuation from study 	Data from Day 1 (post randomization) until start of temporary discontinuation or permanent discontinuation.	While on-treatment	Data will only be used until the start of temporary discontinuation or date of permanent discontinuation. This is to capture that the participant could not tolerate the study treatment as planned.

CCI

CCI

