1.1.2. Secondary Estimand

The primary clinical question of interest is: What is the difference in the proportion of responders (reduction of serum HBsAg levels ≥ 0.5 log IU/mL) from baseline CCI CCI) of GSK3965193 vs. placebo in participants living with chronic hepatitis B prior to prohibited medication use or temporary/permanent discontinuation of treatment?

Attributes of Estimand:

Variable/Endpoint	Treatment	Population	Population Summary
≥ 0.5 log IU/mL reduction in serum HBsAg levels from baseline CCI CCI CCI CCI	GSK3965193 and Placebo	PLWCHB treated on stable NA therapy	Proportion of responders

Intercurrent events will be handled in the same way as the primary endpoint (see Section 1.1.1).

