4.2.2.4. Pharmacodynamic (HBsAg)

Unless otherwise specified, all PD analysis will be reported using PD analysis set.

CCI

CCI

CCI

CCI

CCI

.Following summaries will be provided -

- Summary of Change from Baseline in HBsAg by Visit and Treatment
- Summary of Time to Maximum Reduction in HBsAg

To estimate the mean of maximum reduction of serum HBsAg levels from baseline CCI, a Bayesian approach will be used. This approach will use Gumbel distribution $F(x, \alpha, \beta)$ as the likelihood function for the maximum \log_{10} HBsAg reduction.

For each participant, a non-informative prior will be used with α and β is assumed to be known. The posterior distribution for α will be derived and the posterior probabilities $P(\text{mean of maximum } \log_{10} \text{ HBsAg reduction} \geq \text{cutoff} \mid \text{data})$ will be obtained from the posterior distribution.

CCI

CCI

CCI

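### Part 3 derives the maximum HBsAg reduction as a negative number, but the primary PD analysis asks for the probability that the reduction is at or above a cutoff

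*SAP*

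**What the plan says.** All references are to the Part 3 SAP.

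- **Derivation (4.1.1).** The change at each visit is "Log10 HBsAg at post baseline - Log10 HBsAg at baseline". The maximum reduction in the log10 "HBsAg value is the minimum value of the calculated change from baseline at any post-baseline visit within the specified timeframe".
- **Model (4.2.2.4).** A Gumbel distribution with parameters α and β serves "as the likelihood function for the maximum" log10 HBsAg reduction. On the prior, "a non-informative prior will be used with α and β is assumed to be known". The reported quantity is P(mean maximum reduction ≥ cutoff | data). The value and sign of the cutoff, the value of β and any density formula are not visible.
- **Responder endpoint (1.1.2, repeated in 4.3.1.2.2).** Response is "reduction of serum HBsAg levels ≥ 0.5 log IU/mL", so here a reduction is a positive number.
- **Contrast (1.1.1).** The treatment difference is GSK3965193 minus placebo. Nothing visible says which sign favours GSK3965193.
- **Role (4.1.2, 4.2.3).** The main statistical analyses are Bayesian, and posterior probabilities of passing pre-specified values are to be displayed. No sensitivity analysis is planned for the primary endpoints.

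**The concern.** Section 4.1.1 does more than locate the deepest fall. It says what the maximum reduction is, under the same name that 4.2.2.4 uses for the modelled variable. The two sections need opposite signs. Under 4.1.1 a better response is a smaller (more negative) number. Under 4.2.2.4 and 1.1.2 it is a larger one.

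If the derived variable goes into the model unchanged, the headline probability for a primary PD endpoint no longer measures evidence of effect. The treatment difference has the same problem: an effective drug gives a negative difference under 4.1.1 and a positive one under the reading in 1.1.2 and 4.2.2.4. The version history shows that the derivation was added in SAP Amendment 1 as a clarification, so it is the text that a programmer would be expected to follow.

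**Working it through.** There is no public figure to reproduce, because the Part 3 sample-size text and its operating characteristics are redacted. The check is algebra first, then a simulation on assumed inputs.

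**Step 1: direction, independent of the likelihood.** Let R = log10 baseline minus the lowest post-baseline log10 HBsAg in the window, so that a fall is positive. Section 4.1.1 stores x = −R. Then

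P(mean x ≥ c) = P(mean R ≤ −c).

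- With c = +0.5 this is the probability that the mean reduction is −0.5 or less, that is, that HBsAg stays at least half a log above baseline on average. It is near 0 for any useful drug.
- With c = −0.5 this is the probability that the mean reduction is at most 0.5, the complement of what is wanted.

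**Step 2: the posterior.** For the Gumbel form for maxima with β known and a flat prior on α, t = exp(α/β) has a Gamma posterior with shape n and rate S = Σ exp(−xᵢ/β). The mean of the distribution is α + 0.5772β, so

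P(mean ≥ c | data) = P(t ≥ exp(c/β − 0.5772)).

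With β = 0.3, the threshold for t is exp(1.667 − 0.577) = 2.97 at c = +0.5 and exp(−1.667 − 0.577) = 0.106 at c = −0.5. The form for minima fitted to x is the exact mirror of the form for maxima fitted to R.

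**Step 3: simulation.** R is drawn from a right-skewed Gumbel. Assumed inputs, none of them in the documents: n = 10, β = 0.3, cutoff ±0.5. Average posterior probabilities:

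| True mean reduction (log10) | Intended: P(mean R ≥ 0.5) | x as written, cutoff +0.5 | x as written, cutoff −0.5, form for maxima | x as written, cutoff −0.5, form for minima |
|---|---|---|---|---|
| 1.0 | 1.00 | 0.00 | 0.001 | 0.0002 |
| 0.2 | 0.015 | 0.00 | 0.8 | 0.98 |

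Over a wider grid (n = 5, 10, 15; β = 0.2, 0.3, 0.5; true mean reduction 0.2, 0.5, 1.0), the probability at cutoff +0.5 never averaged above 0.043. At cutoff −0.5 it ran from 0.66 to 1.00 when the true reduction was 0.2 and from 0.00 to 0.11 when it was 1.0, over both Gumbel forms. The direction does not depend on the form.

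**Step 4: the fit, conditional on the form.** If the form for maxima is fitted to x = −R, then S = Σ exp(Rᵢ/β) and the largest reduction dominates: a participant whose reduction is 3β larger than another's carries e³ ≈ 20 times the weight. With R from a Gumbel with known β:

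| n (assumed) | Variable fitted | Bias in mean reduction | Sampling SD | 95% CrI coverage |
|---|---|---|---|---|
| 12 | R | 0.00 | 0.30β | 95% |
| 12 | x = −R | +0.37β | 0.92β | about 58% |
| 4 | x = −R | +0.12β | not needed here | 76% |

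If the form for minima is fitted to x, all of this disappears: no bias and 95% coverage.

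**The case against.** The best defence has three parts.

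**Redaction.** The text around the model in 4.2.2.4 is blacked out, as are a table listed on page 24, within the primary-endpoint section, the protocol's account of this analysis (9.4.2, Part 3) and the sample-size sections. A sign reversal, the Gumbel density and the cutoffs could all be there, and text withheld from the public copy is not missing from the plan. This stands. It limits the point to a contradiction in what can be read.

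**Intent.** Taking the minimum change is a normal way to find the deepest fall. The label in 4.2.2.4, read with the 0.5 log responder rule, shows that a positive reduction is meant. A careful programmer would flip the sign. This also stands as far as it goes, but then 4.1.1 defines the named quantity wrongly and correct results depend on someone departing from it.

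**Gumbel skew.** A reader might infer that the likelihood is skewed the wrong way too, because the Gumbel is often met as a distribution for maxima. The documents do not support that. They name a Gumbel with parameters α and β and no form, and the form for minima would suit the signed change exactly. The bias and coverage figures are therefore conditional. They are also in units of a β that is not public, and the bias is about a third as large at n = 4 as at n = 12.

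**Conclusion.** The contradiction in sign holds. As written, 4.1.1 makes a fall negative, while 4.2.2.4 and 1.1.2 need it positive, and nothing visible connects the two. Followed literally, the reported probability is close to 0 for a positive cutoff and runs against the treatment effect for a negative one. That conclusion follows from algebra and does not depend on the Gumbel form. The probabilities that illustrate it rest on assumed n, β, cutoff and effect.

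The distortion of the fit (mean reduction overstated by about 0.37β and coverage of about 58% at n = 12) is a possibility, present only if the form for maxima is applied to the negative variable.

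A reader might also infer that go/no-go probabilities for the trial are inverted. The documents do not support that. No visible text ties a decision rule to these probabilities, SAP section 2 says that no hypothesis is formally tested, and the reversal may be in redacted text or be made in programming. What is shown is an unreconciled definition of a primary endpoint, with no planned sensitivity analysis that might expose a slip.

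**What to change.** Make three short edits to the Part 3 SAP and carry them into the dataset specification.

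1. **4.1.1:** define R as log10 baseline HBsAg minus the minimum post-baseline log10 HBsAg in the window, positive for a reduction. Use R in the summaries, the likelihood and the treatment difference.
2. **4.2.2.4:** name the Gumbel form for maxima and state that all cutoffs are positive.
3. **1.1.1:** state that a positive GSK3965193 minus placebo difference favours GSK3965193.

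An equivalent choice is to keep the signed change, name the Gumbel form for minima, report P(mean ≤ −cutoff | data), and state that a negative difference favours GSK3965193. Either is sound, provided that one is used throughout.

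If the redacted text already settles the sign and the form, only 4.1.1 needs to be brought into line with it. The cost is a few lines of text and one line of derivation code, with no new data and no change to the design.

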4.1.2. Bayesian Methodology

The main statistical analyses will be carried out using a Bayesian framework.

Prior distributions are specified for each analysis. Posterior mean and 95% credible intervals (CrIs) along with the posterior probabilities of crossing pre-specified values of interest will be displayed, unless otherwise stated.

4.1.3. Baseline Definition

Unless otherwise stated, if baseline data is missing, no derivation will be performed, and baseline will be set to missing.

Table 3 Baseline definition of different parameters for GSK3965193 Monotherapy

Parameters	Study Assessment Visit considered as Baseline for GSK3965193 monotherapy	Derivation of Baseline
12-Lead ECG	Pre-dose Day 1	Average of triplicate ECG measurements
Vital Sign	Pre-dose Day 1	Average of triplicate Vital Sign parameters measurement
Sensory nerve conduction test (SNCV)	Screening, Day -1	The best measurement out of Screening and Day -1 will be considered as baseline, where best being the higher measurement.
Nerve Function	Screening, Day -1	The worst measurement out of Screening and Day -1 will be considered as baseline, where worst being the higher total score.
Cognitive assessment	Day -1 or Prior to dosing Day 1 (whichever is latest)	Single measurement
Clinical laboratory (Chemistry and hematology)	Day -1 or Prior to dosing Day 1 (whichever is latest)	Single measurement
Liver Function	Day -1 or Prior to dosing Day 1 (whichever is latest)	Single measurement
Prothrombin time (PT), international normalized ratio	Day -1 or Prior to dosing Day 1 (whichever is latest)	Single measurement
Urinalysis	Day -1 or Prior to dosing Day 1 (whichever is latest)	Single measurement

Parameters	Study Assessment Visit considered as Baseline for GSK3965193 monotherapy	Derivation of Baseline
Urine albumin-creatinine ratio (ACR)	Day -1 or Prior to dosing Day 1 (whichever is latest)	Single measurement
HBsAg, HBV DNA	Prior to dosing Day 1	Single measurement
CCI	CCI	CCI

Table 4 Baseline definition of different parameters in optional Bepirovirsen monotherapy

Parameters	Study Assessment Visit considered as Baseline for Optional Bepirovirsen arm	Derivation of Baseline
Vital Sign	CCI	Single measurement
Clinical laboratory (Chemistry and hematology)		
Urinalysis	CCI	Single measurement
Urine albumin-creatinine ratio (ACR)		
HBsAg, HBV DNA		

Note: Unscheduled visits prior to dosing will also be considered while deriving baseline.

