### 9.4.1. General Considerations

Unless otherwise specified, baseline will be the last value/assessment before the first dose of study treatment (Day 1 pre-dose). If there are multiple assessments collected at the same scheduled time, the average of these assessments will be used as the baseline.

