6.2.5. Multiple measurements at One Analysis Time Point

When triplicate ECG and/or Vital assessments are taken, mean of the measurement will be calculated first and summary statistics will be based on the calculated mean. This will be applied to both baseline and post baseline assessments.

For lab tests on a study day, if more than one assessment is taken on the same day, the test from a central lab will be taken over the test from a local lab. If multiple assessments are taken from the same type of lab, the worst case will be used.

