4.1.2. Baseline Definition

Baseline is defined as the last non-missing assessment prior to first dose.

For Part 1 periods 1, 2, 3 and 4 and in Part 2B periods 1, 2, and 3 the day 1 pre-dosing assessment will be the baseline. However, if there are no pre-dose assessment collected at Day 1, the last available data from either Day -1 or screening (as schedule of assessment in each Cohort permits) will be defined as baseline. If there are no valid assessments from day 1, day -1 or screening, the baseline will be set to missing.

In Part 1 and 2B period baselines will be defined utilising the assessments taken in the specific period. Participant level baselines will also be computed and will be the means of the available period level baselines for each participant.

For Vital Signs parameters, the pre-dose data is captured as triplicate. In these cases, the baseline will be defined as the mean of the triplicate assessments.

For ECG parameters, except for QTcF, the pre-dose data is captured as triplicate. In these cases, the baseline will be defined as the mean of the triplicate assessments. In Part 1 for both cohorts 1 and cohort 2, baseline QTcF will be based on the mean of 3 pre-dose ECGs collected on Day 1 pre-dose of each treatment period.

In Part 2A, sensory nerve conduction studies at baseline will be collected twice, one at the time of screen and one prior to dosing. Mean (arithmetic mean) of two measurements will be considered as baseline.

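### SAP 4.1.3 gives HBsAg no screening fallback: if the Day 1 sample is lost and there is no unscheduled pre-dose value, a dosed participant has no primary PD result

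*SAP*

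**What the plan says.** The general rule in SAP 4.1.3, which applies where nothing else is specified, is that "if baseline data is missing, no derivation will be performed, and baseline will be set to missing". Table 3 of that section then fixes the baseline visit for each parameter. The row that matters reads "HBsAg, HBV DNA Prior to dosing Day 1 Single measurement". Other rows are wider. Chemistry, haematology, liver function, coagulation, urinalysis and urine ACR may use Day -1 or Day 1 pre-dose, whichever came later, and the nerve tests draw on screening as well as Day -1. A note under the baseline tables allows unscheduled pre-dose visits to count. It does not mention the scheduled screening sample.

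Protocol 9.4.1 states that "baseline will be the last value/assessment before the first dose of study treatment". That sentence opens with a proviso allowing other specifications and closes by identifying the value as Day 1 pre-dose.

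A screening HBsAg exists for everyone. Inclusion criterion 8 (protocol 5.1.3) requires a level above 100 IU/mL, protocol 4.2.3 uses the screening level to decide who is offered bepirovirsen, and SAP 6.1.2 tabulates screening HBsAg categories.

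**The concern.** The primary PD variable has a narrower baseline definition than routine urinalysis. Read literally, an unscheduled draw before dosing can supply the baseline, while the result that admitted the participant to the study cannot.

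The stake is a participant who was randomised, dosed and followed but contributes nothing to the maximum-reduction analysis. Such a participant stays in the PD analysis set, because SAP 3 asks only for one non-missing PD assessment. The visible text gives no imputation for a missing HBsAg baseline and does not say how the participant is counted. SAP 4.2.3 plans no sensitivity analysis that would recover the information.

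**Working it through.** The plan gives no figure on this point, so there is none to reproduce. The check has a textual part and a part on size.

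**Does a missing baseline remove the endpoint?**

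- SAP 4.1.1 defines change at each visit as log10 HBsAg at that visit minus log10 HBsAg at baseline. Maximum reduction is the smallest of these changes in the specified period. With no baseline there is no change and no minimum.
- SAP 4.3.1.2.2 counts a decline of at least 0.5 log10 and/or HBsAg below LLOQ. The decline needs a baseline. Only the below-LLOQ part can be judged without one.
- A value counts as baseline under Table 3 if it is Day 1 pre-dose or unscheduled pre-dose. Screening is neither.

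So the loss needs two conditions together: no Day 1 pre-dose value and no unscheduled pre-dose value.

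**How large is Part 3?** The sample size is redacted. SAP 1.1.3 triggers the supplementary estimand when more than 20% of participants have an intercurrent event, and equates this with four or more.

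- Four must exceed 20%: 4/N > 0.20, so N < 20.
- Three must not: 3/N ≤ 0.20, so N ≥ 15.
- N is therefore 15 to 19, or 20 if four was meant as exactly 20%.

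**Cost of one loss.** As a share of participants: 1/20 = 5.0% to 1/15 = 6.7%.

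The standard error of the treatment difference is proportional to √(1/a + 1/c), with a on active and c on placebo. The allocation ratio is redacted, so 1:1 to 3:1 is assumed.

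| N, ratio | a, c | lose one on active | lose one on placebo |
|---|---|---|---|
| 15, 1:1 | 7.5, 7.5 | +3.8% | +3.8% |
| 15, 3:1 | 11.25, 3.75 | +1.2% | +12.8% |
| 20, 1:1 | 10, 10 | +2.7% | +2.7% |
| 20, 3:1 | 15, 5 | +0.9% | +9.0% |

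Example, bottom right: √[(1/15 + 1/4)/(1/15 + 1/5)] = √(0.3167/0.2667) = 1.090. Fractional arm sizes are kept for scale only.

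**Chance of at least one loss.** This is 1 − (1 − p)^N, where p is the assumed chance that a participant has neither admissible value. The documents give no such rate.

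- p = 1%: 14% (N = 15) to 18% (N = 20)
- p = 2%: 26% to 33%
- p = 5%: 54% to 64%

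**With a screening fallback.** A lost Day 1 sample removes nobody whose screening result is comparable. If HBsAg moved by d log10 between screening and Day 1, that participant's change is off by d and the mean of an arm of n by d/n.

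**The case against.** A reader might infer that the SAP contradicts the protocol. It does not. Protocol 9.4.1 lets the SAP specify otherwise, itself names Day 1 pre-dose, and offers no screening fallback. It follows that the absence of an entry in SAP Table 12 is not clearly an omission. The separate SAP for Parts 1 and 2 does fall back to "the last available data from either Day -1 or screening", but it covers healthy participants with no HBsAg endpoint, so it is weak precedent.

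A reader might also see a conflict over repeat samples, since the protocol says that "the average of these assessments will be used as the baseline" while SAP 6.2.5 says "If multiple assessments are taken from the same type of lab, the worst case will be used". The two address different situations: the protocol averages assessments taken at one scheduled time, and SAP 6.2.5 deals with several laboratory tests on one day. Table 3 calls for a single HBsAg measurement, SAP 6.2.4 has its own priority rule for PD parameters, and no visible text schedules duplicate baseline HBsAg samples. SAP 6.2.5 needs no change on this account.

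The strongest objection concerns the screening value itself. Criterion 8 accepts plasma or serum, whereas the endpoint is serum HBsAg. Protocol 10.2 allows local or central laboratories, and protocol 8 allows qualifying routine-care results from before consent to serve for screening. The screening window is redacted. A sponsor could reasonably prefer a Day 1 baseline to one of mixed origin. This stands as a reason to put conditions on the fallback. It does not justify discarding a comparable result.

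It is also fair that the loss is hypothetical, that no formal hypothesis is tested, and that blacked-out text in SAP 4.2.2.4 or 6.2.4 could hold a handling rule.

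**Conclusion.** The point holds as a conditional weakness. On the visible text, a participant with neither a Day 1 nor an unscheduled pre-dose HBsAg has no primary PD result and no assessable 0.5 log decline, although a screening HBsAg was obtained. Each such loss removes about 5% to 7% of participants. It widens the standard error of the treatment difference by about 1% to 4% if on active and 3% to 13% if on placebo.

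These sizes assume N of 15 to 20, inferred from the SAP 1.1.3 threshold, and allocation between 1:1 and 3:1. The sample is taken before dosing, so its loss has no evident link to treatment, and the expected cost is precision rather than bias. The primary safety endpoints are not affected. The documents do not show that participants are in fact being lost.

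**What to change.** In SAP 4.1.3 Table 3, change the HBsAg and HBV DNA row to: *Day 1 pre-dose; if missing, the last available pre-dose value, including screening, provided it is a serum result from the same laboratory and assay.* Flag participants whose baseline comes from screening, so that the primary result can be read with and without them. Settle this before treatment allocation is known to those choosing the rule.

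The cost is one line of text and one flag variable, with no new samples. The downside is small: for any affected participant the baseline is somewhat older than Day 1. A screening result that fails the condition would still leave baseline missing.
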